#### **4.6 Strategies for Recruitment and Retention**

Subjects will be identified and approached by treating medical oncologists or radiation oncologists in the outpatient clinic. The trial may also be discussed with patients who are admitted to the hospital.

The trial will be listed on the Joint Clinical Trials Office (JCTO) public website and will also be discussed at local professional meetings such as the NY Lung Cancer Learning Center conferences, in order to help generate referrals.

Subjects will not be compensated for taking part in this trial.

## **5. Registration Procedures**

### **5.1 Subject Registration**

Subjects will be registered within the WRG-CT as per the standard operating procedure for Subject Registration.

## **6. Study Procedures**

### **6.1 Schedule of Assessments**

A complete Schedule of Assessments is provided in **Error! Reference source not found.** Prior to performing any trial assessments not part of the subject's routine medical care, the investigator will ensure that the subject or the subject's legal representative has provided written informed consent.

**Table 4. Schedule of Assessments**

Assessment	Screening	Treatment Period										End of Treatment (EOT)	30-day Safety Follow-up	90-day Safety Follow-up	Survival Follow-up
Visit	Screening	C1D1	C1D15	C2D1	C2D15	C3D1	C3D15	C4D1	C4D15	CXD1 and D15	EOT	30-day FU	90-day FU	Every 12 weeks	
Day (d)	(-28~-1)	1(±3d)	1(±3d)	1(±3d)	1(±3d)	1(±3d)	1(±3d)	1(±3d)	1(±3d)	1(±3d)	(within 7 days after determination of treatment discontinuation)	30 days after last dose of trial treatment (±7 d)	90 days after last dose of trial treatment (±14 d)	Every 12 weeks after last dose of trial treatment (±14 d)	
General procedure															
Informed consent 	X														
Inclusion / exclusion criteria	X														
Demography and history of alcohol and tobacco use 	X														
Medical history 	X														
Oncology history 	X														
Prior and concomitant medications and procedures 	X	X										X	X	(X)	(X)
New anti-cancer therapy												X	X	X	X
Overall survival															X
Clinical examination and test															
AE 	X	X										X	X	X	X
Full physical examination 	X	X	X	X	X	X	X	X	X	X	X				
Height (in cm)	X														
Body weight (to the nearest 0.1 kilogram [kg]) 	X	X	X	X	X	X	X	X	X	X	X	X	X		
Vital signs 	X	X	X	X	X	X	X	X	X	X	X	X	X		
12-lead ECG 	X	Clinically indicated										X			
ECOG performance status	X	X	X	X	X	X	X	X	X	X	X	X	X	X	
Cardiac Ultrasonography	X			X	X	X									
Local laboratory test / evaluation															

Immunoglobulin	X													
CPK	X	(X)	X	X	X	X	X	X	X	X				
Hematology test (including reticulocyte) 	X 	(X)	X	X	X	X	X	X	X	X	(X) 	(X) 		
Coagulation test (aPTT, PT, INR)	X 	Clinically indicated												
Serum chemistry 	X 	(X)	X	X	X	X	X	X	X	X	(X) 	(X) 		
Urinalysis 	X 	Clinically indicated									X	(X) 	(X) 	
Serum beta-HCG (if applicable) 	(X) 										(X)			
T3, FT3, FT4 and TSH	X	(X)				X					X 			
Troponin	X	X		X		X		X			X 			
Urine beta-HCG (if applicable) 		(every 12 weeks; or as clinically indicated)												
FSH (if applicable) 	X													
HBV, HCV, HIV 	X													
ANA, ENA 	X													
CRP, IL-6	X	As clinically indicated (IRR, suspected cytokine release syndrome or serum sickness)												
Anti-AChR autoantibody	X													
Anti-MuSK autoantibody	X													
Lymphocytic analysis (B cell count)	X													
Correlative studies														
Multiplex cytokine/chemokine assay for calculation of CYTOX score (as defined by Section 9.1.1)	X	As clinically indicated (IRR, suspected cytokine release syndrome or serum sickness)												
ctDNA 	X	To occur at time of best response and at tumor progression												
Tumor tissue 	X	On-treatment tissue-targeted biopsy if tissue-specific irAE occurs												
TCR sequencing	X	On blood and tissue if tissue-specific irAE occurs												
Peripheral blood for WES	X													
Tumor evaluation														

CT C/A/P 	X	To occur every 2 cycles for the first year, then every 4 cycles for the second year								(X)	(X)	(X)	(X)
PET/CT 	X	To occur at best response, and as clinically indicated											
Brain CT/MRI 	X	(clinically indicated)											
RECIST 1.1	X	Every 8 weeks											
Investigational drug													
KN046 administration 		X	X	X	X	X	X	X	X				

(X) Does not need to be repeated if done within 7 days of C1D1

- 1 Informed consent should be obtained before any trial related procedure and treatment;
- 2 Demographic data include date of birth, sex, race and ethnicity;
- 3 Medical history includes past and concurrent nonmalignant diseases and treatment, past and concurrent malignant diseases and treatment;
- 4 Oncology history includes detailed history of the target indication of this study including histopathological diagnosis, grading and staging in accordance to Masaoka staging; all therapy used for prior treatment of the tumor (including surgery, radiotherapy, chemotherapy, and immunotherapy); any other conditions that were treated with chemotherapy, radiation therapy, or immunotherapy; current cancer signs and symptoms, and AEs effects from current and/or previous anticancer treatments; and current cancer disease status;
- 5 All medications (including herbal medications) taken and procedures performed within 28 days prior to first trial treatment should be recorded; radiation therapy should be recorded;
- 6 All AEs will be collected from time of signature of informed consent through 30 days following the last dose of study drug or the date of subject initiates new anticancer therapy, whichever is earlier. All SAE and treatment related adverse event will be collected from the time of informed consent through 90 days following the last dose of study drug. However, if an investigator learns of any SAE, after 90-day safety follow-up period, and she/he considers there is a reasonable possibility that the event is related to the study drug, the investigator should report to sponsor. All AEs and SAEs should be proactively followed up for each patient, adverse events should be followed to resolution or stabilization at a level acceptable to the investigator.
- 7 Full physical examination includes an examination of general appearance, skin, neck (including thyroid), eyes, ears, nose, throat, lungs, heart, abdomen, back, lymph nodes, extremities, and a basic nervous system evaluation;
- 8 Examination or test results should be obtained within 7 days prior to first trial treatment;
- 9 Vital signs include temperature, respiration rate, pulse rate and blood pressure;
- 10 12-lead ECG will be performed in the supine position after the subject has been breathing quietly for 5 minutes; The ECG results will be used to evaluate heart rate, atrial-ventricular conduction, QR and QT intervals, and possible arrhythmias. Interpretation of the ECG trace must be made by a qualified physician and documented on the ECG eCRF. Each ECG trace should be labeled with the Study Number, Subject Identifier Number, and date, and kept in the source documents at the site;
- 11 Hematology test includes absolute lymphocyte count, absolute neutrophil count, hematocrit, hemoglobin, platelet count, red blood cells, white blood cells and differential count, red blood cell morphology, reticulocytes, mean corpuscular hemoglobin, mean corpuscular volume, mean corpuscular hemoglobin concentration;
- 12 Serum chemistry test includes albumin, alkaline phosphatase, alanine aminotransferase, amylase, aspartate aminotransferase, gamma-glutamyl transferase, blood urea nitrogen/total urea, calcium, chloride, creatine kinase, creatinine, glucose, lactate dehydrogenase, lipase, phosphorus/phosphates, magnesium, potassium, sodium, troponin, total bilirubin, total protein;

- 13 Urinalysis includes bilirubin, blood, glucose, ketones, pH, protein, specific gravity, and color and appearance. If urinalysis is positive for protein, segments and 24-hour urine protein exam should be performed;
- 14 Examination or test results should be obtained before each trial treatment;
- 15 Only be performed when clinically significant abnormal findings are found at EOT visit;
- 16 For women of child bearing potential, a serum pregnant test should be performed within 7 days prior to the first dose of trial treatment. Subsequently, urine beta-HCG test will be monitored every 12 weeks or as clinically indicated. Female subjects who are not considered to be of childbearing potential (for example, age-related natural [spontaneous] amenorrhea  $\geq$  12 consecutive months and increased FSH  $>$  40 mIU/mL), or who are surgically sterile or are sexually inactive, are exempt from pregnancy testing;
- 17 HBV, HCV and HIV tests include HBsAg, HCV and anti-HIV1/2. If HBsAg is positive, HBsAb, HBeAb, HBeAg, HBcAb and HBV DNA should be measured to exclude active HBV infection as clinically indicated; HCV RNA should be tested to exclude active HCV infection If anti-HCV is positive;
- 18 A tumor biopsy should be collected at Screening unless tissue (blocks or slides) from an archival specimen (biopsy or surgery) is available. 10 slides required. On-treatment biopsies would be obtained at time of irAE development if it occurs
- 19 Tumor assessment will be performed using PET/CT at baseline, at time of best response, and when clinically indicated. CT scans of chest, abdomen and pelvis (Chest CT and MRI of Abdomen and Pelvis also acceptable) are also required at baseline, every 2 cycles (8 weeks) for the first year, then every 4 cycles (16 weeks) for the second year. Screening tumor assessment should be performed within 28 days of first trial treatment in order to document baseline status of tumor disease using RECIST 1.1 target and non-target lesions. During treatment period, the tumor assessment visit time window is  $\pm$ 7 days. CT or MRI scan (if MRI is used, CT of chest is mandatory) should always be used in the same modality as the screening period. If a tumor response is documented during the study, confirmation of the response should be performed according to RECIST 1.1, preferably at the regularly scheduled 8-week assessment interval, but no sooner than 4 weeks and no later than 8 weeks after the initial documentation of CR or PR. Confirmation of PR/CR can be done at an assessment later than the next assessment after the initial documentation of PR/CR. If disease progression is documented, confirmation of PD is required, preferably at 8-week assessment interval (but no sooner than 4 weeks and no later than 8 weeks). Tumor assessment will continue until confirmed disease progression per RECIST 1.1, start of new anti-cancer therapy, or withdrawal of informed consent, whichever comes first. If treatment discontinuation is due to reasons other than RECIST 1.1 defined progressive disease, tumor assessment should continue until RECIST 1.1 defined progressive disease, start of new anti-cancer therapy, or withdrawal of informed consent, whichever comes first;
- 20 Brain CT/MRI scan (either, with contrast preferred) is required at screening if not performed within the previous 42 days prior to first trial treatment. During treatment period, brain CT/MRI scan should be done if clinically indicated by development of new specific symptoms;
- 21 Each KN046 will be administered intravenously over at least 90 minutes (90-120 minutes). After the completion of KN046 infusion, subject should be observed at site for at least 2 hours.
- 22 If necessary to confirm postmenopausal status
- 23 Day 1 of each cycle only
- 24 To occur on Day 1 of odd Cycles only
- 25 If ANA or ENA positive, rheumatologic workup indicated.
- 26 Will only repeat ctDNA if genetic alteration detected at baseline.

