#### **2.4.1.1 Immune-related adverse events**

Investigators should be extremely vigilant and be ready to intervene early in the management of irAEs, as the onset of symptoms of irAEs from KN046 treatment (eg, hepatitis) may be subtle. Immune-related AEs have been reported with KN046 and with other anti-PD-1, anti-PD-L1 and anti-CTLA4 antibodies; these are considered consistent with the mechanism of action of immune checkpoint inhibitors.

An immune-related AE can occur shortly after the first dose or several months after the last dose of treatment. All AEs of unknown etiology associated with drug exposure should be evaluated for a possible immune etiology. Efforts should be made to rule out autoimmunity, infection, neoplastic, metabolic disorder, toxin or other etiologic causes prior to classifying an AE as an irAE.

Management guidelines to irAE are provided. Exclusion criteria E09, E10 and E11 will be applied to exclude susceptible subjects. During the study, routine hematologic, chemistry (including creatine phosphokinase) and immune safety assays (including AChR autoantibody and anti-MuSK autoantibody if clinically indicated) are performed at baseline, during the treatment phase and 30- and 90-day safety follow-up. Vital signs and physical examinations are closely monitored according to the study protocol.

From Phase I data of KN046-AUS-001, the most frequent treatment-related adverse events included arthralgia (16.7%), fatigue (14.8%), infusion-related reaction (14.8%), diarrhea (11.1%) and pruritus (11.1%). Skin and subcutaneous tissue disorders and musculoskeletal and connective tissue disorders were the most frequent irAEs. The TRAE and irAEs were not found to occur in a dose-dependent manner up to 5 mg/kg

Q2W, and neither the number nor severity of TRAE or irAEs was exacerbated due to dose escalation at the RP2D or lower levels.

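### Table 4 footnote 15 withholds the 30- and 90-day hematology and chemistry from patients with a normal end-of-treatment visit, contrary to Sections 2.4.1.1 and 6.1.4

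*Combined protocol and SAP*

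**What the plan says.** Three places in the protocol govern blood tests after treatment ends.

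- **Table 4, footnote 15.** The last two filled cells of the "Hematology test (including reticulocyte") row, and of the serum chemistry row, are a bracketed X with footnote 15: "Only be performed when clinically significant abnormal findings are found at EOT visit".
- **Section 2.4.1.1.** The measures against immune-related adverse events (irAEs) include "routine hematologic, chemistry (including creatine phosphokinase) and immune safety assays", which "are performed at baseline, during the treatment phase and 30- and 90-day safety follow-up". The only qualifier, clinical indication, is attached to the two autoantibody tests.
- **Section 6.1.4.** The safety follow-up list includes a blood count and a metabolic panel with no condition. In the same list, coagulation depends on clinical indication, and urinalysis and thyroid tests are referred to the schedule.

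On timing, Section 2.4.1.1 warns: "An immune-related AE can occur shortly after the first dose or several months after the last dose of treatment". It also asks for vigilance "as the onset of symptoms of irAEs from KN046 treatment (eg, hepatitis) may be subtle".

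**The concern.** A site working from Table 4 would draw no routine blood at 30 or 90 days from a patient with a normal EOT visit. A site working from Section 2.4.1.1 or 6.1.4 would.

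The condition also runs against the protocol's own reasoning. If irAEs may begin months after the last dose and hepatitis may start quietly, a normal result at EOT does not clear a patient through day 90. Appendix A grades immune-related hepatitis by ALT/AST and nephritis by creatinine, so a case without symptoms is visible only on a blood test.

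Two things are at stake: detection of late laboratory-only irAEs, and the laboratory-change review in Section 12.4.2. Under footnote 15, scheduled values after EOT would come only from patients with an abnormal EOT visit, which is a selected subset.

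**Working it through.** **1. What each source gives a patient with a normal EOT visit**

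| Source | Day 30 | Day 90 |
|---|---|---|
| 2.4.1.1 | Hematology, chemistry, CPK | Hematology, chemistry, CPK |
| 6.1.4 (visits not named separately) | Blood count, metabolic panel | Blood count, metabolic panel |
| Table 4, cells counted left to right | Conditional, so not done | No mark |
| Table 4, aligned with the urinalysis row | Conditional, so not done | Conditional, so not done |

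Column placement is uncertain in the text available to me. A literal count of the 14 cells puts the two footnote-15 marks under EOT and 30-day. The urinalysis row has a plain X followed by two footnote-15 marks, which points to 30- and 90-day. That reading is more plausible, because a test at EOT can hardly depend on findings at EOT. On either reading, neither visit has an unconditional hematology or chemistry mark.

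**2. Does Table 4 take precedence?** The clause deferring to the schedule is in the heading of Section 6.1.2.1 and covers Day 1 visits. In 6.1.4 only urinalysis and thyroid tests defer to it. Section 3.1 refers laboratory assessments to Section 6, which contains both Table 4 and 6.1.4.

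**3. CPK.** The separate CPK row shows no follow-up mark in the extracted text. Footnote 12 includes creatine kinase in serum chemistry, so under Table 4 a follow-up value could come only through the conditional panel. Section 2.4.1.1 names CPK; Section 6.1.4 does not.

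**4. Timing of the gate.** Section 3.1 places EOT within 14 days of the last dose, or 14 × 24 = 336 h. Mean terminal half-life at 5 mg/kg Q2W is 181.8 h (Table 2-6) and 157.4 h (Table 2-13). Then 336 / 181.8 = 1.85 and 336 / 157.4 = 2.13, so EOT falls within about two half-lives. Day 90 is at least 90 − 14 = 76 days later.

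**5. Visits affected.** The plan's expected sample size at a 5% response rate reproduces: 10 + 19 × (1 − 0.95^10) = 17.624. With two visits per patient and full attendance:

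- stop after stage 1: 2 × 10 = 20
- expected at a 5% response rate: 2 × 17.624 = 35.2
- expected at 20%: 10 + 19 × (1 − 0.8^10) = 26.96, and 2 × 26.96 = 53.9
- maximum: 2 × 29 = 58

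These count visits, not harm.

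**The case against.** The best counter-argument is that both opposing sections are weak evidence of intent. Section 2.4.1.1 is background, and its cross-references do not fit: it cites exclusion criteria E09 to E11 as screening out susceptible patients, but criterion 10 concerns prior malignancy and criterion 11 intercurrent illness. The list in 6.1.4 is repeated item for item in 6.1.5, although Section 3.1 describes survival follow-up as contact for survival status, so the missing condition may be a template leftover. Aligning both sections with Table 4 would also remove the conflict. That much stands: the direction of the correction is a judgement. The contradiction remains, and the stated late and subtle onset of irAEs favours testing.

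Mitigation also counts. Table 4 marks vital signs, weight and ECOG status through day 90. Footnote 6 collects serious and treatment-related events to day 90 and requires active follow-up. Unscheduled tests remain possible. These help with symptomatic events, less with laboratory-only ones.

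A reader might infer three stronger points that the documents do not support:

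- **A calculable number of missed irAEs.** The irAE term for raised transaminases occurred in 3 of 30 patients at 5 mg/kg Q2W in KN046-AUS-001 (none Grade 3 or higher) and 0 of 45 in KN046-CHN-001. Scaled to 29 patients, that is 3/75 × 29 = 1.16 to 3/30 × 29 = 2.9 at any time. Assuming that 5% to 25% start after EOT gives 0.05 × 1.16 = 0.06 to 0.25 × 2.9 = 0.73. That range rests on one of several hepatic terms and an onset share the documents do not give. It counts events that start late, not events missed.
- **No clinical examination at follow-up.** The "Full physical examination" row in Table 4 appears to end at EOT, but 6.1.4 and 6.1.5 both list the examination, and the row carries the same extraction risk as the laboratory rows.
- **The metabolic panel in 6.1.4 means the footnote 12 panel.** Sections 6.1.2.1 and 6.1.2.2 name CPK and troponin beside the metabolic panel, so the term appears narrower there.

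**Conclusion.** The contradiction is real and does not depend on how the Table 4 columns are read. Section 2.4.1.1 carries most of the weight, because it alone names the 30- and 90-day visits and CPK; 6.1.4 supports it through its unqualified listing. Two laboratory visits per patient, at most 58 in total, are promised in one place and withheld in another for patients with a normal EOT visit.

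The effect is confined to safety monitoring and the laboratory safety summary; the response endpoint and the two-stage design are untouched. The number of irAEs missed cannot be estimated from the documents. It is likely small, given at most 29 patients and the other follow-up in place. The correction is worth making because footnote 15 removes a safety measure the protocol relies on, and restoring it is cheap.

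**What to change.** In Table 4:

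- Replace the bracketed X with footnote 15 by a plain X for hematology and serum chemistry at the 30-day and 90-day visits. A bare bracketed X should not remain, because the legend ties that symbol to tests done within 7 days of C1D1.
- Confirm a plain X at EOT for both rows, in line with Section 6.1.3.
- Keep footnote 15 for urinalysis only, where 6.1.4 already defers to the schedule.

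In Section 6.1.4, add CPK by name to match 2.4.1.1, and leave the term metabolic panel undefined there.

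The cost is an amendment to two table rows and one list entry, and at most two routine draws per patient (maximum 58) at visits already scheduled. The draws would be run as the Table 4 serum chemistry panel, which is wider than 2.4.1.1 strictly names: it also includes troponin, amylase and lipase.

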##### **Important potential risks:**

- Immunogenicity (anti-KN046 antibody formation);
- Embryo fetal toxicity

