##### **4.2 Inclusion Criteria**

1. Signed informed consent form;
2. Male or female, 18 years of age or older; willing and able to complete all required procedures of study;
3. Pathologically confirmed diagnosis of thymic carcinoma; a tumor sample is required for confirmation of pathological diagnosis and further studies on the tumor tissue (see correlative science Section 9)
4. Inoperable or metastatic disease;
5. Progressive disease documented in the last 6 months
6. Has failed platinum-based chemotherapy, with progression either during or after treatment
7. Had failed at least one regimen of systemic therapy containing immune checkpoint blockade therapy targeting PD-1, PD-L1, or CTLA-4 for locally advanced unresectable or metastatic disease. Subjects should have documented progressive disease while or after an immune checkpoint therapy. If subjects discontinued therapy due to reasons other than progressive disease, subjects should have completed at least 2 cycles of immune checkpoint therapy
8. Baseline measurable disease according to RECIST 1.1. Target lesions situated in a previously irradiated area are considered measurable if progression has been demonstrated in such lesions;
9. ECOG performance status of 0 or 1;
10. Adequate organ function assessed within 7 days prior to first trial treatment:
  - Hematological function
    - i. ANC $\geq$ 1.5 x 10^9/L;
    - ii. Hemoglobin $\geq$ 9 g/dL;
    - iii. Platelets $\geq$ 100 x 10^9/L;

- Renal function
  - i. Calculated creatinine clearance $\geq$ 60 mL/min (Cockcroft-Gault method);
- Hepatic function
  - i. Total bilirubin $\leq$ 1.5 x ULN (or 2.5 x ULN for documented Gilberts' syndrome);
  - ii. ALT/AST $\leq$ 3.0 x ULN (or 5.0 x ULN for documented liver metastasis);
- INR or aPTT  $\leq$ 1.5 x ULN;

11. Have a life expectancy of at least 3 months;
12. If female of childbearing potential, have a negative serum pregnancy test within 7 days prior to first trial treatment;
13. If female of childbearing potential or a male subject with a partner with childbearing potential, be willing to use a highly effective method of contraception (with a failure rate of less than 1.0% per year) from first study treatment to 24 weeks after completion of the trial treatment.

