  - Clinically significant (that is, active) cardiovascular disease: cerebral vascular accident/stroke (< 6 months prior to enrolment), myocardial infarction (< 6 months prior to enrolment), unstable angina pectoris, congestive heart failure (New York Heart Association Classification Class II-IV) or serious cardiac arrhythmia requiring medication (including corrected QT interval prolongation of  $> 470$  msec calculated according to Fridericia and/or pacemaker or prior diagnosis of congenital long QT syndrome;
12. Persisting toxicity related to prior therapy (including any prior investigational therapy) of CTCAE  $\geq$  grade 2 (NCI-CTCAE v5.0) or related toxicity not recovery to baseline, with the exception of alopecia of any grade;

13. Prior allo-HSCT or solid organ transplant;
14. Known severe hypersensitivity reactions to antibody drug ( $\geq$  grade 3 NCI-CTCAE v5.0), any history of anaphylaxis, uncontrolled asthma (that is, 3 or more features of partially controlled asthma), or any history of severe drug hypersensitivity (for example immune mediated liver toxicity, immune mediated thrombocytopenia or anemia);
15. Is pregnant or breastfeeding;
16. Other medical conditions that at the discretion of investigator interfere with the requirements of the trial in terms of safety or efficacy evaluation, or treatment compliance. These include but are not limited to psychiatric or substance abuse disorder, moderate to large pleural fluid/cardiac effusion/ascites, or recurrent/refractory pleural fluid/cardiac effusion/ascites.
17. Subjects with history or baseline positive antiacetylcholine receptor (AChR) autoantibody and anti-MuSK autoantibody
18. Subjects who developed grade 3 or above immune related AE which could not be managed by steroid or immune suppressant will be excluded

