#### **6.1.1 Screening Visit (28 days before start of treatment)**

During the Screening period and before any trial-related investigations and assessments are started, subjects will be asked to sign the informed consent form (ICF). The Screening procedures and Baseline assessments will be completed within 28 days of signing the ICF before first trial treatment.

The subjects' information that will be documented during Screening includes the demographic information (date of birth, sex, race and ethnicity) and the complete medical history (oncology history, previous and ongoing medications, prior surgery, radiation and medication therapies, and baseline medical condition etc). The AE reporting period for safety surveillance and a concomitant medication recording period begins when the subject first signs an informed consent.

During Screening, subjects will undergo a complete physical examination, vital signs, recording height and body weight, 12-lead ECG, and a determination of the ECOG performance status.

During Screening, pathology reports will be reviewed to confirm diagnosis.

The Screening laboratory examination includes hematology, coagulation, serum chemistry, anti-AChR autoantibody, anti-MuSK autoantibody, immunoglobulin, urinalysis, troponin, B cell count, neutrophil count, lymphocyte count, Cardiac ultrasonography, total T3, free T3, free T4 and TSH will also be assessed at Screening for all subjects. Viral tests for HBV, HCV and HIV should be performed at Screening.

During Screening, a serum beta-human chorionic gonadotropin pregnancy test will be performed for females of childbearing potential. Females who are postmenopausal or who have undergone hysterectomy or bilateral oophorectomy are exempt from pregnancy testing. If necessary to confirm postmenopausal status, FSH will be drawn at Screening.

During Screening, the tumor evaluation will be performed using CT scan or MRI or any other established methods. A brain CT/MRI scan is required at Screening if not performed within 42 days prior to first trial treatment.

Failure to establish subject eligibility due to laboratory parameters is allowed to be re-tested following consultation with the Medical Monitor.

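### Footnote 16 of the Schedule of Assessments exempts sexually inactive women from pregnancy testing, while inclusion criterion 12 and section 6.1.1 require a serum test for every woman of childbearing potential and list no such exemption

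*Combined protocol and SAP*

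**What the plan says.** Four places in the combined protocol and SAP bear on this.

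- **Section 4.2, inclusion criterion 12:** "If female of childbearing potential, have a negative serum pregnancy test within 7 days prior to first trial treatment". The criterion carries no exception.
- **Section 6.1.1, Screening Visit:** "a serum beta-human chorionic gonadotropin pregnancy test will be performed for females of childbearing potential". The exemption follows: "Females who are postmenopausal or who have undergone hysterectomy or bilateral oophorectomy are exempt from pregnancy testing". Sexual inactivity is not in that list.
- **Table 4, footnote 16:** the footnote opens with "For women of child bearing potential, a serum pregnant test should be performed within 7 days prior to the first dose of trial treatment". It then sets urine testing every 12 weeks or as clinically indicated. It closes by exempting women not considered to be of childbearing potential, and also those "or who are surgically sterile or are sexually inactive, are exempt from pregnancy testing". The footnote is attached to both the serum and the urine beta-HCG rows of the table.
- **Section 2.4.1, important potential risks:** the list includes "Embryo fetal toxicity".

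**The concern.** The schedule and the eligibility criterion give different answers for the same woman. One who is fertile but reports no sexual activity must have a negative serum result under criterion 12 and must be tested under section 6.1.1, yet footnote 16 releases her from testing. The protocol states no order of precedence between the schedule and the eligibility section.

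If the footnote is followed, two things result. She can receive KN046 without the result that was a condition of entry, although fetal exposure is a risk the protocol names. She is also an eligibility deviation, created by following the protocol's own schedule. Because this is a single-center trial, one local reading of the footnote could apply to every subject.

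**Working it through.** No sample size, error rate or estimate enters here, so the check is a comparison of texts.

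**Step 1. Apply each passage to one case: a woman of childbearing potential who is sexually inactive.**

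| Passage | Serum test before first dose? |
|---|---|
| Section 4.2, criterion 12 | Required, negative, within 7 days; no exception |
| Section 6.1.1, screening | Required; she is in none of the listed exempt groups |
| Footnote 16, opening sentence | Required within 7 days |
| Footnote 16, closing sentence | Exempt |

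The closing sentence of footnote 16 conflicts with the other two passages and with the footnote's own opening sentence.

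**Step 2. Ask whether sexual inactivity could be meant as one form of lacking childbearing potential.** The footnote names women not of childbearing potential, gives menopause with raised FSH as its example, and then adds surgical sterility and sexual inactivity after the word or. As written, these are further groups. No passage defines childbearing potential so as to leave out sexually inactive women. If such a definition were read in, it would carry consequences elsewhere: the contraception requirement in inclusion criterion 13 applies to women of childbearing potential, so the same woman would fall outside that requirement too. Nothing in the protocol suggests that this is intended.

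**Step 3. Ask whether another criterion closes the gap.** Exclusion criterion 15 (section 4.3) bars a subject who "Is pregnant or breastfeeding", but it names no test and so does not settle whether a sexually inactive woman must have one.

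**Step 4. Separate the entry test from the on-treatment test.** The 12-weekly urine test appears only in its Table 4 row and in footnote 16. Criterion 12 concerns entry, and section 6.1.1 concerns screening. Exempting a sexually inactive woman from the urine test therefore contradicts no other passage. What is unclear is only whether a corrected exemption list would apply to that test as well.

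**Step 5. Size.** The protocol gives no expected age or sex mix for its 29 subjects, so the number of women affected cannot be derived. It could be zero.

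**The case against.** The strongest reply is that criterion 12 is unconditional, that review of the inclusion and exclusion criteria is itself a screening item in Table 4, and that section 6.1.1 repeats the test. A site applying the criteria strictly would find an untested woman ineligible. This stands to the extent that dosing without a test is a possibility, dependent on the footnote being followed, and not a certainty. It does not remove the contradiction.

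Three stronger readings are tempting, and the documents do not support them.

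- **That the exemption removes the only protection against fetal exposure.** Other safeguards remain: exclusion criterion 15, contraception under criterion 13 until 24 weeks after treatment, provision in Table 4 for urine testing when clinically indicated, withdrawal from KN046 on pregnancy (section 8.1) and reporting within 24 hours (section 13.1.7). What the footnote lifts is scheduled testing.
- **That each exempted woman misses about eight urine tests.** That figure needs the full two years: 104 / 12 = 8.7, or eight complete intervals. Median duration of therapy in the two phase I trials was 11 and 12 weeks (sections 2.3.2.1.1 and 2.3.2.2.1), and 12 / 12 = 1, so about one scheduled test is the more typical count. As step 4 shows, the urine exemption is in any case not in conflict with another passage.
- **That the surgical sterility exemption also breaches criterion 12.** The term may be wider than the two operations named in section 6.1.1, but no passage shows that a surgically sterile woman counts as being of childbearing potential. It is a difference in wording that a single list would tidy, not a demonstrated conflict.

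It is also fair to say that sexual inactivity is a current status. A woman who becomes active no longer meets the exemption as worded, so the possibility of change during treatment does not by itself create a conflict.

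**Conclusion.** The inconsistency is real and can be seen by reading the three passages together. Footnote 16 exempts a woman whom criterion 12 and section 6.1.1 require to be tested before first dose. The consequence, a fertile woman dosed without the negative result needed for entry, is conditional on the site following the footnote. The number of women concerned is unknown and probably very small.

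The primary response analysis is not affected: the Efficacy Analysis Set (section 12.4.4) rests on centrally confirmed diagnosis and at least one treatment, not on this test. The reason to act is that the conflict lies in an entry condition tied to a named risk and is cheap to remove.

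The conclusion rests on reading sexual inactivity as a separate ground for exemption, which is how the footnote is written, and on the absence of any definition of childbearing potential that says otherwise. It takes no view on which testing rule is the right one.

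**What to change.** Reconcile inclusion criterion 12, section 6.1.1 and footnote 16 to a single list of who is exempt from pregnancy testing, and have all three refer to it. The result should be that the schedule cannot exempt a woman whom the eligibility criterion requires to be tested. In the same edit, define childbearing potential once and state whether the list also governs the 12-weekly urine test. Which groups belong on the list is for the investigator and sponsor to decide.

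The cost is a short wording change through a protocol amendment. For the entry test, applying criterion 12 as it stands adds nothing beyond a serum test the criterion already requires. Any further cost arises only if the agreed list also extends the urine schedule, and then for very few women.
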